### SAE Reporting by a Paper Form

1. SAE reporting on a paper report form is used as a back-up method for an electronic data capture system failure. The form includes completion instructions for the Investigator, names, addresses, and telephone and fax numbers. All information from the paper form will be transcribed into the electronic form as soon as the system becomes available.
2. Facsimile transmission (fax to mail) of the paper form or any follow-up information is the preferred method for transmission and will be done within 24 hours to the Sponsor or its designee.
3. In rare circumstances and in the absence of facsimile equipment, notification by telephone is acceptable with a copy of the form sent by overnight mail or courier service.
4. Initial notification via telephone does not replace the need for the Investigator to complete and sign the form within 24 hours after becoming aware of the event.
5. Additional documents (e.g. laboratory reports, autopsy report, hospital discharge letter) and relevant pages from the eCRF may be required in addition (e.g. medical history, concomitant medication). The data provided will be consistent with the information in the eCRF.

### Recording and Reporting of DLTs

1. Each event that meets the DLT criteria, as specified in Section 6.6.3, will be recorded in the eCRF within 24 hours after awareness of the event.
2. Serious DLTs will be reported in an expedited manner, using the SAE reporting process, as specified above.
3. Notification of each DLT related event (non-serious and serious) will be reported to the Sponsor or its designee within 24 hours from the date of awareness.

### Reporting of AESIs

1. For a non-serious AESI, the site will complete the specific AESI report form and notify the Sponsor immediately (within 24 hours), using the same process for reporting SAEs, as specified above.
2. For a serious AESI, the site will complete an SAE report form, using the SAE reporting process, specified above.

[figure not shown]
### Reporting of Pregnancies

1. Pregnancy will be reported whether related to the study intervention using the applicable paper form.
2. The applicable form will be used to report if an abnormal outcome of the pregnancy occurs and the child/fetus sustains an event.
3. Facsimile transmission (fax to mail) of the paper form or any follow-up information is the preferred method for transmission and will be done within 24 hours to the Sponsor or its designee.

## Appendix 8 BOIN Design

In Section 9.4.2.1 the BOIN design by [Yuan 2016](#) is introduced. The target toxicity for this study is 30%; the maximum total number of participants for the Safety Run-in is 12 (maximum number of participants for a certain dose level is 6). The respective boundaries are provided in [Yuan 2016](#) (Table 1 in that article and the figure below) as well as the rules for escalation and de-escalation (see Table 2 in that article and the respective table in Section 9.4.2.1 in this protocol) will be used. [Yuan 2016](#) also performed simulations to investigate the operation characteristic of the BOIN design in comparison to other designs for certain situations (see Figure 3 in that article).

### Flowchart of the BOIN design

\* DLT rate = 
$$\frac{\text{Total number of patients who experienced DLT at the current dose}}{\text{Total number of patients treated at the current dose}}$$

## Appendix 9      Protocol Amendment History

The information for the current amendment is on the title page.

### Protocol Amendment Summary of Changes

#### Protocol History

Version Number	Type	Version Date
1.0	Original Protocol	27-Apr-2020
1.1-USA	Country-specific Amendment	30-Jul-2020
1.2-FRA	Country-specific Amendment	06-Oct-2020

**Country-specific Amendment Version 1.2-FRA to Protocol Version 1:****Protocol Version [1.2 FRA] (06 October 2020)**

This amendment is substantial based on the criteria in Article 10(a) of Directive 2001/20/EC of the European Parliament and the Council of the European Union.

**Overall Rationale for the Amendment**

Changes made to improve the clarity of the study in line with comments raised by IEC/IRBs and national regulatory authorities.

Section # and Name	Description of Change	Brief Rationale
5.1 Inclusion Criteria	To criterion #2, and clarified that advanced tumors are also unresectable.	Updated to clarify tumors are unresectable to better reflect the requirements of the patient population.
5.2 Exclusion Criteria	Added new criterion, #16, "History of ILD or interstitial pneumonitis including radiation pneumonitis that required steroid treatment."	Exclusion of patients with a history of interstitial lung disease (ILD) or interstitial pneumonitis to better reflect the requirements of the patient population
6.5.4 Special Precautions 6.5.4.1 Cetuximab	Wording updated under Eye disorders.	Updated to align with the wording from the EU Summary of Product Characteristics (SmPC) for cetuximab.
6.5.4 Special Precautions 6.5.4.2 Tepotinib	Added specific details for edema.	Provided detailed guidelines according to the severity grade of the toxicity observed, and the recommended for tepotinib dose modifications.
6.6 Dose Selection and Modification 6.6.2 Tepotinib	Added further clarification under the tepotinib treatment interruption section to include recommended dose modifications in case of adverse reactions of clinical interest.	Provided detailed guidelines according to the severity grade of the toxicity observed, and the recommended for tepotinib dose modifications.
6.7 Study Intervention after the End of the Study	Added details on provision of providing study intervention after the End of the Study.	Updated to specify the terms for the free of charge provision of study intervention for participants who benefit at the End of the Study.
7.1 Discontinuation of Study Intervention	Updated this section to clarify further in event of QTcF findings.	QTc interval prolongation were added as reasons for discontinuation of study intervention. Additionally, the initiation of close and appropriate ECG monitoring in hospital according to local standards is referred to.
Appendix 8 Country-specific Requirements	Reference to changes described in this table.	Administrative update.
Appendix 9 Protocol Amendment History	Refers to changes made to previous local country specific amendments.	Administrative update.
Appendix 10 Sponsor Signature Page	Clinical study protocol version updated.	Administrative update.

Section # and Name	Description of Change	Brief Rationale
Appendix 11 Coordinating Investigator Signature Page	Clinical Study protocol version updated.	Administrative update.
Appendix 12 Principal Investigator Signature Page	Clinical study protocol version updated.	Administrative update.

**Country-specific Amendment Version 1.1-USA to Protocol Version 1:****Protocol Version [1.1 USA] (30 July 2020)****Overall Rationale for the Amendment**

The purpose of this amendment is to incorporate FDA request received on 06 July 2020, and on 24 July 2020.

Section # and Name	Description of Change	Brief Rationale
1.1 Synopsis	Removed "if applicable" after Cohort B	Update for clarification on Health authority feedback.
1.2 Schema	Removed "and might be initiated at a later time point" after Cohort B will include US participants only	
2 Introduction	Added text "The proposed administered dose of 500 mg tepotinib corresponds to 500 mg tepotinib hydrochloride hydrate and is equivalent to 450 mg tepotinib (free base form) throughout the document. The 250 mg tepotinib corresponds to 250 mg tepotinib hydrochloride hydrate and is equivalent to 225 mg tepotinib (the free base form)."	Health authority feedback to revise the protocol to clarify the amount of tepotinib free base administered.
2.1 Study Rationale	Removed "if Cohort B is initiated"	Update for clarification on Health authority feedback.
4.1 Overall Design	Removed "if Cohort B is initiated"	Update for clarification on Health authority feedback.
5.1 Inclusion Criteria	To criterion #2, added that left-sided CRC tumors, "from splenic flexure to rectum." Made reference to current National Comprehensive Cancer Network (NCCN) CRC v4.2020 guidelines	Health authority feedback to define left sided tumors.
	To criterion #7b, added "First-line treatment must include a fluoropyrimidine and oxaliplatin or irinotecan and second-line treatment must include a fluoropyrimidine, oxaliplatin, or irinotecan."	Health authority feedback to clarify that first-line treatment must include a fluoropyrimidine and oxaliplatin or irinotecan and second-line treatment must include a fluoropyrimidine, oxaliplatin, or irinotecan.

Section # and Name	Description of Change	Brief Rationale
5.2 Exclusion Criteria	Added to criterion #8 as point "g. Corrected QT interval by Fridericia (QTcF > 480 ms)"	Health authority feedback to clarify that we exclude patients with QTc intervals >480 msec.
	Added new criterion, #16, "History of ILD or interstitial pneumonitis including radiation pneumonitis that required steroid treatment."	Health authority feedback for exclusion of patients with a history of ILD or interstitial pneumonitis.
6.1 Study Intervention(s) Administration	Added, "and if local cetuximab label requires", a corticosteroid is given prior to the first infusion of cetuximab	Health authority feedback to acknowledge the difference between USA and outside the USA requirements related to premedication. To specify the use of corticosteroids will be based on local requirements.
6.5.1 Permitted Medicines	Added, "and if local cetuximab label requires", a corticosteroid is given prior to the first infusion of cetuximab	
6.6.3 Dose Limiting Toxicity	Added "Grade 4 vomiting or diarrhea" as DLT criteria.	Health authority feedback to implement that that DLT criteria will be revised so Grade 4 (life threatening) vomiting or diarrhea are considered as DLT criteria.
9.2 Sample Size Determination	Removed "if applicable" after Cohort B, and removed "if initiated" after Cohort B	Health authority feedback addressed to clarify that enrollment of Cohort B is now targeted to initiate immediately in the USA, and not possibly later as initially implied.
Appendix 2 Study Governance	Under study administrative section, deleted "(sites in North America will only be included if Cohort B is initiated)"	
Appendix 6 Clinical Laboratory Tests	Added phosphorus to biochemistry parameters for assessment.	Health authority feedback in the study monitoring plan to include assessment of phosphorus in the biochemistry panel.

MSC2156119J, MSB0010442D  
MS202202-0002

Phase II single arm study of tepotinib combined with  
cetuximab

ATC	Anatomical Therapeutic Chemical classification
BMI	Body Mass Index
BOR	Best Overall Response
BSA	Body Surface Area
BUN	Blood Urea Nitrogen
CDISC	Clinical Data Interchange Standards Consortium
CHMP	Committee for Medicinal Products for Human Use
CI	Confidence Interval
COVID-19	Coronavirus disease 2019
CR	Complete Response
(e)CRF	(electronic) Case Report Form
CSR	Clinical Study Report
CTMS	Clinical Trial Management System
CV	Coefficient of variation
DLT	Dose Limiting Toxicity
DoR	Duration of Response
ECG	Electrocardiogram
ECOG	Eastern Co-operative Oncology Group
EGFR	Epidermal growth factor receptor
FAS	Full Analysis Set
FLC	Free Light Chain
FU	Follow-up

GFR	glomerular filtration rate
ICH	International Conference on Harmonization
IAP	Integrated Analysis Plan
ICH	International Conference on Harmonization
IPD	Important Protocol Deviation
IRC	Independent Review Committee
LLN	Lower Limit of Normal
LLOQ	Lower limit of quantification
MDRD	Modification of Diet in Renal Disease
MedDRA	Medical Dictionary for Regulatory Activities
MRI	Magnetic Resonance Imaging
NA	Not Applicable
NCI-CTCAE	National Cancer Institute – Common Terminology Criteria for Adverse Events
OR	Objective Response
ORR	Objective Response Rate
PD	Progressive Disease
Pd	Pharmacodynamics
PFS	Progression Free Survival
PR	Partial Response
PT	Preferred Term
PK	Pharmacokinetics
PP	Per Protocol
QD	Once Daily
PR	Partial Response
RECIST	Response Evaluation Criteria in Solid Tumors
RP2D	Recommence Phase II Dose
SAE	Serious Adverse Event
SAF	Safety
SCR	Screening analysis population
SD	Stable Disease
StDev	Standard Deviation

SDTM	Study Data Tabulation Model
SI	International System of Units
SMC	Safety Monitoring Committee
SOC	System Organ Class
TEAE	Treatment-Emergent Adverse Event
ULN	Upper Limit of Normal
WHO-DD	World Health Organization Drug Dictionary

3 Modification History

Unique Identifier for Version	Date of IAP Version	Author	Changes from the Previous Version
1.0	10 Mar 2021	PPD	First version

4 Purpose of the Integrated Analysis Plan

The purpose of this Integrated Analysis Plan (IAP) is to document technical and detailed specifications for all the analyses of data collected for protocol MS202202_0002.

Results of the analyses described in this IAP will be included in the Clinical Study Report (CSR) or in separate reports. Additionally, the planned analyses identified in this IAP may be included in regulatory submissions or future manuscripts. Any post-hoc, or unplanned analyses performed to provide results for inclusion in the CSR but not identified in this prospective IAP will be clearly identified in the CSR.

The IAP is based upon Section 9 (Statistical considerations) of the Protocol version 1.0 dated 27 April 2020 and is prepared in compliance with ICH E9. It describes analyses planned in the protocol.

Details on outputs used to support review of the study by a Safety Monitoring Committee (SMC) during the safety run-in period are available in the SMC Charter.

5 Objectives and Endpoints

[figure not shown]
Safety Run-in

Objectives	Endpoints (Outcome Measures)	IAP section
Primary		
To confirm the recommended Phase II dose (RP2D) of tepotinib when used in combination with cetuximab	Occurrence of dose limiting toxicities (DLTs)	Section 15.1

Overall Study

Objectives	Endpoints (Outcome Measures)	IAP section
Primary		
To evaluate the preliminary efficacy of tepotinib (RP2D) in combination with cetuximab in terms of tumor response	Objective response (OR, confirmed complete response [CR] or partial response [PR]) determined according to RECIST Version 1.1 assessed by the Investigators	Section 14.1
Secondary		
To further evaluate the efficacy of the combination of tepotinib (RP2D) and cetuximab in terms of duration of response (DoR)	DoR (months) according to RECIST Version 1.1 assessed by the Investigators.	Section 14.2.1
progression-free survival (PFS)	PFS (months) according to RECIST Version 1.1 assessed by the Investigators.	Section 14.2.2
overall survival (OS)	OS (months) assessed by the Investigators.	Section 14.2.3
To evaluate the safety and tolerability of tepotinib in combination with cetuximab	
Occurrence of Adverse Events (AE) and treatment-related AEsOccurrence of clinically significant changes in vital signs, laboratory parameters and 12-lead electrocardiogram (ECG) findings	Section 15
To characterize the immunogenicity of cetuximab	Immunogenicity of cetuximab as measured by antidrug antibody (ADA) assays on Day 1 Cycle 1 and End of Treatment Visit	Section 14.2.4

CCI

Objectives	Endpoints (Outcome Measures)	IAP section
CC1		

6 Overview of Planned Analyses

This IAP covers the analyses for efficacy, safety, CCI and CCI data to be performed for the primary and final analyses. More details about each specific analysis are provided in the subsections below.

Statistical analyses will be performed on the basis of CDISC SDTM data. These SDTM data contain as clean as possible eCRF data as well as external data including laboratory data, biomarker data, and tumor assessment results by Investigator.

A data review meeting will be held prior to any database lock. In addition, no database can be locked until this IAP has been approved.

6.1 Analyses for SMC meetings

The primary safety endpoint (i.e. the occurrence of DLTs during the first treatment cycle of the safety run-in period) will be evaluated during SMC meetings and based on participant profiles. More details are provided in the SMC Charter.

The Safety Monitoring Committee (SMC) will decide on dose escalation, dose de-escalation, expansion of the current dose level, or suspension of enrollment based on safety and, if available, PK data. In the safety run-in period, at least 6 treated participants on a dose level are regarded as necessary to confirm the RP2D of tepotinib. Cohorts of 3 participants will be enrolled. SMC meetings will take place after 3 treated participants within a dose-specific cohort completed the first cycle. On request additional SMC meetings might take place. Participants who are not DLT evaluable will be replaced. Once all participants of the respective dose-specific cohort have completed the DLT period or discontinued from trial prematurely, a data snapshot will be taken for provision of SMC participant profiles. There will be no data cut-off applied.

The SMC will decide and confirm the recommended Phase II dose (RP2D) of tepotinib to be used in combination with cetuximab. The SMC may also decide to reduce the tepotinib dose to 250 mg QD based on the data collected during the safety run-in and for the whole study.

6.2 Interim analysis for futility

A futility analysis will be performed after the first 12 participants are enrolled for second line (2L) treatment (Cohort A). The date 13 weeks after the first dose date (the scheduled time point of the second scan, C5D1, including a time window of 7 days) of the 12th patient enrolled will be used here as cut-off date. Recruitment of further participants into this study, both cohorts, will continue. If there are less than 2 responders (confirmed CR or PR) within the first 12 participants treated with RP2D, the enrolment of 2L participants for this study might be stopped for futility.

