Activity / Assessment	Screening / Baseline	Intervention Period (in cycles of 3 weeks)									EoT	Safety Follow up / Discontinuation	Survival Follow-Up / EoS / 1-Year Follow-Up	Notes
	Day -56 to Day -1	Cycle 1 (21 days)		Cycle 2 (21 days)		Cycle 3 and subsequent cycles (21 days)		Within 14 days after decision to withdraw IMP	30 days after the last dose	After Safety Follow-Up, every 3 months, up to 1-year Site Visit or by Telephone				
Cycle Day		1	8	15	1	8	15	1	8	15				
Visit Window		± 3 days			± 3 days			± 3 days				- 3 to + 7 days	± 1 month	
ctDNA sample	X							Cycle 3, 5, 9 and 13 only			X			Collection predose (within 60 min prior to tepotinib dose), before premedication, if applicable (See Appendix 4)
Documentation of RAS/BRAF wild-type status, and high MET amp levels	X													Confirmed prior to enrollment and after disease progression on the previous anti-EGFR therapy by an established test.
Tepotinib until PD or intolerance		QD												Decided by the Sponsor and SMC: Dosing may be stopped at any time to review safety and PK data and allow for adjustments before dosing is resumed. Additional schedules may also be evaluated.
Cetuximab until PD or intolerance		Weekly (Day 1)												See Section 6.1 for details of premedication required prior to first infusion.

Activity / Assessment	Screening / Baseline	Intervention Period (in cycles of 3 weeks)									EoT	Safety Follow up / Discontinuation	Survival Follow-Up / EoS / 1-Year Follow-Up	Notes
	Day -56 to Day -1	Cycle 1 (21 days)		Cycle 2 (21 days)		Cycle 3 and subsequent cycles (21 days)		Within 14 days after decision to withdraw IMP	30 days after the last dose	After Safety Follow-Up, every 3 months, up to 1-year Site Visit or by Telephone				
Cycle Day		1	8	15	1	8	15	1	8	15				
Visit Window		± 3 days		± 3 days		± 3 days			- 3 to + 7 days		± 1 month			
Tumor Assessment (RECIST Version 1.1) based on MRI and/or CT scans and other protocol-defined imaging modalities.	X							X #)					See Section 8.1 Screening tumor assessment needs to happen within 28 days prior to dosing. All evaluations should be documented by the Investigator and images uploaded to the imaging repository, for a possible independent read at a later date. #): C3, C5, C7, C9, C11, C13, C15 and subsequently every 4 cycles until study closure, or disease progression regardless of study intervention modifications/discontinuation. If disease progression is not certain, consider continuing to image.	

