Cytology results will be collected when available. Enlarging pleural/pericardial effusion and/or ascites (fluid collections) may or may not denote progression. The radiologist can utilize cytology findings (if available) to decide if significant new fluid or unequivocal and significant enlarging fluid is an indication of progression.

The Investigator may perform scans in addition to a scheduled study scan for medical reasons or if the Investigator suspects PD. Participants who withdraw from the study for clinical or symptomatic deterioration before objective documentation of PD will be requested to undergo appropriate imaging to confirm PD. Every effort should be made to confirm a clinical diagnosis of PD by imaging according to RECIST Version 1.1.

Participants will be assessed every 6 weeks starting from Cycle 3 Day 1 visit until 9 months, and every 12 weeks thereafter according to RECIST Version 1.1, until disease progression, death, withdrawal of consent, or study closure. Details on how to perform RECIST Version 1.1

assessments are provided in [Appendix 5](#). Investigator assessments will be conducted. Any CR or PR should be confirmed, preferably at the scheduled 6-week interval or at the next scheduled imaging visit, but no sooner than 4 weeks after the initial documentation of CR or PR. In the case of symptoms suggesting progression, participants should be evaluated by imaging thereafter for documentation and confirmation of the tumor responses.

The same method of assessment and the same technique should be used to characterize each identified and reported lesion at Baseline and during the study. If a chest X-ray indicates metastatic disease while the participant is enrolled in this study, a CT of the chest is required for confirmation. All assessments should be provided by the same physician or radiologist if possible during the study.

Participants who withdraw from the treatment for reasons other than progressive disease will have additional visits for tumor assessments every 6 weeks until 9 months, and every 12 weeks thereafter until disease progression. A  $\pm$  7-day time window is permitted for these additional follow-up visits until 9 months, and  $\pm$  14 days thereafter. Reasons for study termination should be recorded if this visit is the last visit for the participant. Recording of any new anticancer therapy will be made (a tumor assessment is mandatory before initiating the new therapy).

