9.1 Data Handling After Cut-off Date

By its nature, data after cut-off may be incomplete and subject to further change and will not be used for summary statistics, statistical analyses, listings or imputations.

Stop dates are not affected by this rule, e.g. a stop date of AEs, which starts prior to the cut-off, but stops after date of cut-off, will not be changed.

These rules will be applied to all analyses performed for the interim analysis for futility and main analysis. For the final analysis no cut-off date will be applied: the analysis will be performed only after all the data have been collected, fully cleaned and the database has been locked.

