14.1 Primary Endpoint (Overall Study): Objective Response

14.1.1 Derivation and analysis

Best Overall response (BOR) will be assessed based on reported overall responses at different evaluation time points from the study treatment start date until documented disease progression in accordance to RECIST v1.1 by investigator, taking requirements for confirmation into account as detailed below.

Only tumor assessments performed before the start of any subsequent anti-cancer therapies will be considered in the assessment of BOR. If a tumor assessment was performed on the same day as start of new anti-cancer therapy, it will be assumed that the tumor assessment was performed prior to the start of the new anti-cancer therapy, therefore the tumor assessment will be included in the assessment of BOR.

Clinical deterioration will not be considered as documented disease progression. The date of the overall response assessment is the earliest date for imaging of target, non-target and new lesions of images taken at that response assessment.

BOR Based on Confirmed Responses:

- Complete Response (CR) = at least two determinations of CR at least 4 weeks apart (with no PD in between)
- Partial Response (PR) = at least two determinations of PR or better (PR followed by PR or PR followed by CR) at least 4 weeks apart (and not qualifying for a CR), with no PD in between
- Stable Disease (SD) = at least one SD assessment (or better) \geq 6 weeks after start date (and not qualifying for CR or PR).
- Non-CR/non-PD (applicable only to participants with non-measurable disease at baseline) = at least one non-CR/non-PD assessment (or better) \geq 6 weeks after start date (and not qualifying for CR or PR).
- Progressive Disease (PD) = PD \leq 12 weeks after start date of study treatment (and not qualifying for CR, PR, non-CR/non-PD or SD).
- Not Evaluable (NE): all other cases.

SD can follow PR only in the rare case that tumor increases by less than 20% from the nadir, but enough that a previously documented 30% decrease from baseline no longer holds. If this occurs the sequence PR-SD-PR is considered a confirmed PR. A sequence of PR – SD – SD – PD would be a best response of SD if the minimum duration for SD definition has been met.

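### Cohort A futility rule: the protocol makes the stop binding and the SAP makes it optional, and the SAP's 13-week cut-off cannot count a response first seen at week 12 in the latest-dosed participants

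*SAP*

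**What the plan says.** **Protocol 9.2 (Cohort A).** Success is 5 or more confirmed responders in 22. The stated probabilities are 80.8% at a true rate of 30% and 5.7% at 10%, with a futility look at 12 participants included in the calculation. With fewer than 2 responders in the first 12, second-line enrolment *will* be stopped. The stated stopping probabilities are 8.5% at 30% and 65.9% at 10%.

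**SAP 6.2 and 14.1.3.** The threshold is the same: "If there are less than 2 responders (confirmed CR or PR) within the first 12 participants treated with RP2D". Both sections say, however, that enrolment *might* be stopped. The data cut-off for the 12th participant is "13 weeks after the first dose date (the scheduled time point of the second scan, C5D1, including a time window of 7 days". Meanwhile, "Recruitment of further participants into this study, both cohorts, will continue".

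**SAP 9.1.** Data after the cut-off "will not be used for summary statistics, statistical analyses, listings or imputations", and "These rules will be applied to all analyses performed for the interim analysis for futility and main analysis".

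**Confirmation.** SAP 14.1.1 defines a confirmed PR as "at least two determinations of PR or better (PR followed by PR or PR followed by CR) at least 4 weeks apart". Protocol 8.1.1 asks for confirmation "preferably at the scheduled 6-week interval or at the next scheduled imaging visit, but no sooner than 4 weeks after the initial documentation" of the response. The Protocol 1.3 imaging schedule is "C3, C5, C7, C9, C11, C13, C15 and subsequently every 4 cycles", which puts the first three scans at weeks 6, 12 and 18.

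**The concern.** There are two separate problems in one rule.

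First, the documents disagree on whether the stop is binding. The protocol's figures describe a mandatory stop, and the SAP describes a discretionary one. A reader of the SAP cannot tell which operating characteristics apply.

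Second, the cut-off admits the week-12 scan but cannot credit a response first found on it in the last participants dosed. Such a response is scored as a non-response. The error can only lower the count, in a rule that may close Cohort A. Nothing in the SAP tells the decision maker to look for a response awaiting confirmation.

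**Working it through.** **1. Reproduce the stated figures** (Protocol 9.2: n = 12 then 22, thresholds 2 and 5, p = 0.30 or 0.10; every responder among the 12 known at the look).

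P(criterion met) = P(Bin(12, p) ≤ 1):
- p = 0.30: 0.0138 + 0.0712 = 8.50% (stated 8.5%)
- p = 0.10: 0.2824 + 0.3766 = 65.90% (stated 65.9%)

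Binding stop: P(success) = Σ over x = 2 to 12 of P(Bin(12, p) = x) × P(Bin(10, p) ≥ 5 − x):
- p = 0.30: 80.84% (stated 80.8%)
- p = 0.10: 5.69% (stated 5.7%)

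The protocol arithmetic is right for a binding rule with complete response status.

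**2. Stop never exercised:** P(Bin(22, p) ≥ 5).
- p = 0.30: 80.843 + 2.702 = 83.545, i.e. 83.5%
- p = 0.10: 5.685 + 0.528 = 6.213, i.e. 6.2%

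The added terms are the trials with fewer than 2 of 12 that still reach 5 of 22.

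**3. Timing** (days from first dose). The cut-off is 13 × 7 = day 91 for the 12th participant, so someone dosed d days earlier has 91 + d days of follow-up. The week-12 scan is day 84. Confirmation is possible at 84 + 28 = day 112 at the earliest, which needs d ≥ 21. On schedule it is week 18, day 126, which needs d ≥ 35. Even a scan 7 days early (day 77) confirms no sooner than day 105, so the 12th participant is affected whatever the accrual.

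**4. Size.** The documents give neither accrual nor response timing. Assumptions: evenly spaced dosing every s days, scheduled scans, and a share w of eventual confirmed responders first responding at week 6 (w = 0.9 to 0.5), the rest at week 12. The number affected, k, is the count of i ≥ 0 with i × s < 35: k = 1 for s ≥ 35, k = 2 for 17.5 ≤ s < 35, k = 3 for 11.7 ≤ s < 17.5.

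Responders visible at the look = Bin(12 − k, p) + Bin(k, p × w). For k = 1:

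P(visible < 2) = P(Bin(11, p) = 0) + P(Bin(11, p) = 1) × (1 − p × w)
- p = 0.30: 0.0198 + 0.0932 × 0.73 = 8.78% (w = 0.9); 0.0198 + 0.0932 × 0.85 = 9.90% (w = 0.5)
- p = 0.10: 0.3138 + 0.3835 × 0.91 = 66.28%; 0.3138 + 0.3835 × 0.95 = 67.82%

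| Affected | P(criterion met), true 30% | P(criterion met), true 10% |
|---|---|---|
| 0 (as stated) | 8.50% | 65.90% |
| 1 | 8.78-9.90% | 66.28-67.82% |
| 2 | 9.07-11.51% | 66.67-69.75% |
| 3 | 9.37-13.35% | 67.05-71.68% |

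**5. Binding stop applied at the SAP cut-off.** P(≥5 of 22) at a true 30% becomes 79.98-80.67% with one affected and 77.65-80.30% with three, below the stated 80.8%.

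**The case against.** The strongest case for leaving the plan alone is that the cut-off looks deliberate. It sits at the second scan plus its window, so week-6 responses can be confirmed. The word *might* leaves room for judgement on immature data. The study is open-label and investigator-assessed, tests no hypothesis (Protocol 9.1), and reports everything descriptively. In the only guaranteed case, one affected participant, the shift at a true 30% is 0.3 to 1.4 points. About 342 screened for at most 48 treated, with a staggered run-in, also makes fast Cohort A accrual less likely, although no rate is given.

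Most of this stands as to size. It does not remove the point. Discretion helps only if someone is told to look for a pending response, and no section says so. SAP 9.1 excludes later data from the futility look, listings included. Protocol 9.2 also uses these probabilities to justify n = 22. The difference in verb is not explained by the SAP being based on Protocol version 1.0: the version 2.0 change log for section 9.2 mentions no change to the stop rule, and SAP section 7 describes only COVID-19 impact.

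A reader might infer more than the documents support:
- *That 8.5%/65.9% are miscalculated.* They reproduce exactly for complete response status.
- *That the trial will stop more often than stated.* They are lower bounds on meeting the criterion. Under an optional rule they do not bound actual stopping.
- *That week-12 responses are lost in all 12 participants.* Only the 12th and those dosed shortly before are affected.
- *That a type I error rate is inflated.* No significance level is set; 5.7% and 6.2% are descriptive decision probabilities.

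**Conclusion.** Both parts hold, and both are minor.

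The conflict between *will* and *might* is a plain inconsistency and needs no assumptions: 80.8%/5.7% belongs to a binding stop and 83.5%/6.2% to a stop never exercised. It is tempting to say that an optional stop must lie between these pairs. That is not safe at the SAP cut-off, because a stop acted on with incomplete data can take the 30% figure below 80.8%.

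The undercount is certain in direction and, for the 12th participant, certain to exist. Its size depends on accrual and on the week-6 share, which are assumptions here. Slow accrual leaves it close to the stated figures. With three affected and half of responders first seen at week 12, the chance of meeting the criterion at a true 30% is about 13% instead of 8.5%.

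**What to change.** **(a) One verb, matching figures.** Use the same verb in SAP 6.2, SAP 14.1.3 and, at the next amendment, Protocol 9.2. Quote 80.8%/5.7% with 8.5%/65.9% if the stop is binding, or 83.5%/6.2% if it is not exercised. State that all of these assume complete response status.

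**(b) A conditional hold in SAP 6.2 and 14.1.3.** Keep the 13-week cut-off and add: if confirmed responders are fewer than 2 but confirmed plus pending responders among the first 12 are at least 2, no futility decision is made until the next scheduled scan of the pending participants, and that scan is counted as an exception to section 9.1. Pending means a CR or PR documented by the cut-off, not yet confirmed, with no PD and no subsequent anti-cancer therapy. The requirement of at least 2 matters: with none confirmed and one pending, waiting cannot change the result.

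If every eventual confirmed responder first responds by week 12 and is confirmed by the scans then counted, the probability of meeting the criterion returns to 8.5%/65.9%. Later first responses or later confirmations (for example PR-SD-PR) are still missed, and the figures otherwise remain lower bounds.

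**Cost.** One SAP sentence, plus the wording and figures in (a). Counting only pending responses that later confirm, the frequency of a hold is the excess over the stated figures in working step 4. With one affected it is 0.3-1.4% of looks at a true 30% and 0.4-1.9% at 10%; with three, 0.9-4.9% and 1.2-5.8%. Pending responses that fail to confirm add to this. The delay is about 3 to 6 weeks: 112 − 91 = 21 days if the 12th participant's confirmation scan is brought forward to the earliest permitted day, 126 − 91 = 35 on schedule, 42 with a 7-day window. Recruitment continues meanwhile, so a 42-day hold could use about 1 Cohort A place at 5-week spacing (42/35 = 1.2) or 3 at 2-week spacing (42/14). The chance of meeting the criterion at a true 10% falls slightly, towards 65.9%.
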